2.1.2 Secondary Objectives

- To evaluate whether the intervention is effective in increasing education staff and parents' self-efficacy in managing children's challenging behaviour.
- To evaluate whether the intervention is effective in reducing the self-reported burnout of education staff.
- To examine in which contexts and through which mechanisms the group works to achieve these outcomes.

2.2 ENDPOINTS

2.2.1 Primary Endpoint

The primary outcome measure is the short form version of the Depression Anxiety and Stress Questionnaire (DASS-21).

2.2.2 Secondary Endpoints

The secondary outcome measures are as follows:

- The Challenging Behaviour Self-Efficacy Scale (CBSES)

- Copenhagen Burnout Inventory (CBI) (Education staff only)
- Comprehensive Assessment of Acceptance and Commitment Therapy Processes (ComPACT)
- Workshop Evaluation Measure (WEM)

3 STUDY DESIGN

- The study has a mixed-methods design and draws upon a realist evaluation framework. The mixed methods approach allows the utilisation both quantitative and qualitative approaches to gain a greater level of detail than either one methodology would allow for individually, and for the results to support a firmer conclusion if the differing methodologies corroborate each other. The realist evaluation approach is a relatively new framework for research and aims to answer “what works for whom in what circumstances” (Pawson & Manzano-Santaella, 2012, p.177). Realist evaluation tends to critique randomised controlled trials and other evaluations as overly focused on aggregate outcomes which evaluate interventions in a binary way as successful or unsuccessful. Realist evaluation suggests that it might be more helpful to consider the context in which the intervention has been implemented and how this has interacted with mechanisms to produce the outcomes observed. This framework has been chosen to guide the mixed-methods approach in this study as it is particularly relevant given the complexity of delivering psychological interventions in this population, and the many factors that may influence their effectiveness.
- Participants may be involved in the study for a period of approximately six months, due to the expectation that they may need to wait for a group appropriate to them to begin. Participants will be actively involved in the group for nine weeks, with three weeks of group sessions, and a focus group six weeks after this.
- The study will take place in NHS Lothian buildings, schools or in community facilities.

4 STUDY POPULATION

4.1 NUMBER OF PARTICIPANTS

- We will aim to recruit approximately 40 participants to the study (10 participants allocated to four groups).
- Number of sites involved: 8 (LD-CAMHS and up to 7 schools for children with special educational needs).
- Length of recruitment period: Estimated at approximately six to eight months.

4.2 INCLUSION CRITERIA

- Parent or Guardian of a Child aged 5-18 with a diagnosis of an Intellectual Disability/Learning Disability and experience of challenging behaviour.
- OR an employee working in a school for children with additional support needs, directly working with children with diagnosed Intellectual/Learning Disabilities.
- Must speak English fluently.
- Must be able to provide informed consent.

4.3 EXCLUSION CRITERIA

- Temporary staff members (contract remaining of less than six months).
- Parents or Education Staff aged less than 18 years old.

- Parents or Education staff that have a diagnosis of an ID, such that they would not be able to understand the group materials or questionnaires and complete them independently.
- Individuals who are not able to provide informed consent.

4.4 CO-ENROLMENT

Participants' direct care team or school are likely to be aware of whether they are participating in other research. However, participants will additionally be routinely verbally asked about this during their discussion with study researchers, the direct care team or school. Where other studies are observational and questionnaire-based only in nature, this will be permitted. However, participants will not be permitted to take part in other intervention research during the duration of the study.

5 PARTICIPANT SELECTION AND ENROLMENT

5.1 IDENTIFYING PARTICIPANTS

LD-CAMHS clinicians (members of the direct care team) will directly identify potential participants from patients currently on their caseloads. This may involve the patient file being reviewed by the clinician to ensure that the parents would meet the study inclusion criteria, and/or a telephone call or face to face discussion with potential participants. Clinicians will record their communication with potential participants, regarding the study, within the clinical notes. This will allow other clinicians within their care team to know if parents have already been approached.

Schools will identify current staff members that may benefit from participating in the study. This may involve a review of staff files to identify whether they meet study inclusion criteria (e.g. that have employment contract of sufficient duration) but will not involve any review of their medical records. Schools may distribute study information sheets to staff members and ask them to discuss it with a named member of staff if interested in participating or may discuss with individual staff members who meet study criteria. Schools will also distribute information sheets to parents or guardians of children who attend the school, who meet the study criteria. This may involve review of files regarding the child/parent that the school may hold (but not their medical files).

Flyers advertising the study, its group locations and times will be placed in the LD-CAMHS building and in school buildings (should the relevant management authorities wish to do so) and may be distributed to participants also. The flyers will serve to heighten awareness of the research study and as a reminder of the next group dates available.

The direct care team and school staff will be informed of the study, and inclusion and exclusion criteria through meetings, emails and telephone calls as appropriate.

5.2 CONSENTING PARTICIPANTS

The process of taking informed consent will be LD-CAMHS clinicians or senior education staff members providing the potential participant with the participant information sheet and discussing this with them. The participant information sheets for the study provide clear, easy to understand information to support potential participants making an informed decision where they are aware of the possible risks and benefits to participating. Considering the suggested heritability of milder forms of ID, it will be important to ensure that participants, particularly parents, have the capacity to give informed consent. This will be based on the referring clinician/school staff's judgement, as the individuals who will know the potential participants best. Potential participants will then take a minimum of 24hours to decide whether to participate in the study or not, to try to reduce any pressure they may feel regarding their participation. Should participants decide to take part in the study, they will be asked to return their completed

contact details form to their clinician or senior education staff member who discussed the study with them. It will be made clear that by completing and returning the form, they are consenting to these details being passed to the study research team who will contact them to discuss the study. When the study research team receive the contact details form, they will telephone the participant to discuss any questions they may have and to discuss their availability to attend a group. Before the beginning of the first group session, participants will complete the study consent form with the study researchers on an individual basis. This will ensure that the study research team can make sure that participants are fully informed about their decision to participate in the study.

5.2.1 Withdrawal of Study Participants

Participants are free to withdraw from the study at any point or a participant can be withdrawn by the Investigator. If withdrawal occurs, the primary reason for withdrawal will be documented in the participant's case report form, if possible. The participant will have the option of withdrawal from

- (i) all aspects of the trial but continued use of data collected up to that point
- (ii) all aspects of the trial with removal of all previously collected data

Participants who do not attend one or more of the group sessions will be welcome to attend the remaining sessions if they so wish but will be excluded from any relevant analyses. Participants may take part in the focus group if they have attended at least one group session.

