6 STUDY ASSESSMENTS

6.1 STUDY ASSESSMENTS

Participants will complete measures at three time points: before the first group session, after the last group session and before the focus group approximately six weeks after the last group session.

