6.2 LONG TERM FOLLOW UP ASSESSMENTS

Participants will be invited to take part in an hour-long focus group approximately six weeks after the therapeutic group has ended. This focus group will be facilitated by a researcher, who may be LD-CAMHS clinician, to reduce the impact of a social desirability bias in participants' responses. Parents and education staff will attend separate focus groups. There will be no further follow-up after the focus group. Participants will be asked to complete the follow-up measures just before the focus group takes place. If participants do not attend the focus group, questionnaires will be posted to their home address with a return envelope provided, or they may return them to their LD-CAMHS clinician or participating school.

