8 STATISTICS AND DATA ANALYSIS

8.1 SAMPLE SIZE CALCULATION

Power calculations were performed utilising G-Power 3.1 (Faul et al., 2007). The statistical analysis was set to be a with a within-between interaction, with two groups and three measurement points. The alpha level was set to 0.05 and power to 0.80, as per convention (Cunningham & McCrum-Gardner, 2007). The effect size previously reported for psychological distress in a similar study (McConachie et al., 2014) was medium to large. To be conservative, the power calculation for this study was performed with a medium effect size ($f=0.25$), which suggested a total sample size of 28 participants. Therefore, this study will aim to have four groups with ten participants each. This would mean recruiting 40 participants, with the expectation that 12 would be lost to attrition.

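### No withdrawal option keeps questionnaire follow-up, and participants who miss a session without withdrawing are followed up but then excluded from analysis

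*Combined protocol and SAP*

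**What the plan says.** Section 5.2.1 gives two forms of withdrawal. The first is from "all aspects of the trial but continued use of data collected up to that point"; the second is from "all aspects of the trial with removal of all previously collected data". They differ only in what happens to scores already collected, and neither leaves room for further questionnaires.

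The same section treats missed sessions separately. Participants who miss one or more "will be welcome to attend the remaining sessions if they so wish but will be excluded from any relevant analyses". They also remain eligible for the focus group: "Participants may take part in the focus group if they have attended at least one group session".

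Section 6.1 sets the schedule: "Participants will complete measures at three time points", namely before the first session, after the last, and about six weeks later. Section 6.2 provides a fallback for the last of these: "If participants do not attend the focus group, questionnaires will be posted to their home address with a return envelope provided". Return through the clinician or school is also allowed, and no attendance condition is attached. The questionnaire table in section 7.1 shows a postal route only in the final column, not for the measures at session 3.

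Section 8.1 plans for 40 recruited "with the expectation that 12 would be lost to attrition". Section 8.2 assumes missing at random and imputes when less than 5% is missing. Above that, it promises to examine the mechanism and then impute by a method not yet named.

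**The concern.** The primary outcome is self-reported distress, and the protocol's account of risks and benefits (section 1) accepts that taking part may itself cause some distress. A person who leaves because the workshop upset them, or did not help, is one whose later DASS-21 score matters most. Sections 3, 4.1 and 8.1 describe no untreated comparison group, so the effectiveness claim rests on change within people, and selective loss of later scores feeds directly into that change.

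Some of the loss looks avoidable. The postal machinery exists, and some people who no longer want the sessions may be willing to fill in a battery that section 7.1 puts at up to fifteen minutes. The right to have data deleted is an ethical choice and is not in question here.

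**Working it through.** **Who loses scores, and by which rule**

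| Participant | Six-week questionnaires sent? | Scores in the analysis? | Rule responsible |
|---|---|---|---|
| Formally withdraws, data kept | No | Only earlier scores, and none if a session was missed | 5.2.1, first option; exclusion sentence |
| Formally withdraws, data removed | No | None | 5.2.1, second option |
| Misses a session, does not withdraw | Yes, at or in place of the focus group (6.2) | No, for the relevant analyses | 5.2.1, exclusion sentence |
| Attends all sessions, misses the focus group | Yes, by post (6.2) | Yes, if returned | none |

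So two separate rules remove scores. A third withdrawal option alone would recover little: a person who used it to stop sessions would have missed at least one, and the exclusion sentence would still remove them. Both rules have to change.

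**The plan's own figures**

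Inputs from section 8.1: two groups (k = 2), three measurements (m = 3), f = 0.25, alpha 0.05, power 0.80. The correlation ρ between repeated measures and the sphericity factor ε are not given; ρ = 0.5 and ε = 1 are assumed.

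- Noncentrality λ = f² × N × m × ε / (1 − ρ) = 0.0625 × 28 × 3 / 0.5 = 10.5.
- Degrees of freedom: (k − 1)(m − 1) = 2 and (N − k)(m − 1) = 52.
- Power is 0.812 at N = 28 and 0.778 at N = 26, so the stated 28 reproduces.
- 12/40 = 30%, and 28/(1 − 0.30) = 40, so the recruitment target reproduces.
- The 28 depends on the assumed ρ: the required N is 54 at ρ = 0, 38 at 0.3, 18 at 0.7 and 12 at 0.8.

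On the reproducing assumptions, power would be 0.854 with 31 analysed and 0.888 with 34. The planned 28 already gives about 81%, so lost power is not the problem.

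**Bias, as an illustration**

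Let the 12 leavers have a mean change worse than the 28 completers by d, in SD units. Suppose r of them, representative of the 12, supply full scores that are analysed. The mean over all 40 differs from the completers' mean by d × 12/40; the mean over those analysed differs from it by d × r/(28 + r). The bias is

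d × [12/40 − r/(28 + r)].

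| Recovered r | Bracket | d = 0.25 | d = 0.5 | d = 1.0 |
|---|---|---|---|---|
| 0 | 0.300 | 0.075 | 0.150 | 0.300 |
| 3 | 0.300 − 3/31 = 0.203 | 0.051 | 0.102 | 0.203 |
| 6 | 0.300 − 6/34 = 0.124 | 0.031 | 0.062 | 0.124 |

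Both d and r are assumptions; the documents support no value for either.

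**Whether imputation repairs it**

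If the 12 keep their earlier data and each misses at least one of three assessments, at least 12/120 = 10% of DASS-21 assessments are missing. That falls in the higher branch of section 8.2. The check promised there can compare leavers and completers on observed scores, but it cannot show whether loss depends on distress that was never measured. Nor can imputation help participants who are excluded by rule or whose data are deleted.

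**The case against.** The strongest reply is that a reader might infer from section 5.2.1 that anyone who stops the workshop loses follow-up. The documents do not support that. Missing sessions is not withdrawal, and section 6.2 posts the six-week questionnaires to anyone absent from the focus group. The gap in data collection is confined to formal withdrawers; for other non-attenders the loss comes from the exclusion sentence. This stands, and it is why the point is framed as two rules.

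A reader might also infer that the change would lift complete data from 28 to 31–34. That does not follow either. Attrition may include missed-session exclusions and unreturned forms as well as withdrawals, and the existing postal route supplies only the last of three assessments. A leaver using it would have a baseline and a six-week score but not a complete set.

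The plan also has partial safeguards: the reason for withdrawal is recorded where possible, the percentage missing is reported, and missingness is examined. These make the loss visible but do not recover the scores.

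Finally, the consent form was not available for this review and may already offer a partial option. If so, section 5.2.1 should say so.

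**Conclusion.** The point holds in a limited form and is worth acting on. Formal withdrawers lose later primary-outcome scores that some might willingly return, and people who miss a session but stay are measured and then set aside. Both rules move the estimate towards completers of the workshop.

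That the loss is selective is a reasonable inference, not something the documents show; leavers could also be people who had improved. The amount of bias is unknown. The figure of 0.15 SD, falling to about 0.10 or 0.06 SD, requires leavers to be 0.5 SD worse than completers, all 12 losses to be otherwise unobserved, and those recovered to be representative and fully measured. It should be read as an order of magnitude. It would be wrong to conclude that the study is underpowered on this account, since 12 losses are already allowed for.

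**What to change.** 1. Add a third option to section 5.2.1 and, if it is not already there, to the consent form: stop the sessions but complete the remaining questionnaires. Keep both existing options, including deletion.
2. Extend postal return in section 6.2 and the section 7.1 table to the post-session-3 measures, so that a leaver can supply all three assessments.
3. Amend the missed-session exclusion so that the main analysis keeps all available scores whatever the attendance, and make the full-attendance analysis a sensitivity analysis. Without this, the first two changes bring in few usable data.
4. Report the number and timing of withdrawals with data removal, since their scores cannot be analysed.

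The cost is a minor amendment, changes to protocol and possibly consent wording, some postage and follow-up effort. The estimated effect may also be smaller, because participants who did not complete the workshop would count in it.

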2 STUDY OBJECTIVES

2.1 OBJECTIVES

2.1.1 Primary Objective

- To evaluate whether an ACT and PBS based workshop ("the intervention") is effective in reducing the psychological distress experienced by parents and education staff who work with children with Intellectual Disability.

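### Anyone who misses a group session is excluded from analysis and no all-participant analysis is planned, so the primary DASS-21 result would most naturally describe full attenders only

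*Combined protocol and SAP*

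**What the plan says.** The protocol and SAP are one document. Section 5.2.1 lets people who miss one or more group sessions carry on, but with a consequence: they "will be welcome to attend the remaining sessions if they so wish but will be excluded from any relevant analyses". It does not say which analyses are relevant. The next sentence makes an allowance for the qualitative part: "Participants may take part in the focus group if they have attended at least one group session".

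Section 6.1 sets the measurements "before the first group session, after the last group session and before the focus group approximately six weeks after the last group session". On the last of these, section 6.2 adds: "Participants will be asked to complete the follow-up measures just before the focus group takes place". People who do not come to the focus group are sent the questionnaires by post.

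Section 8.2 plans a repeated-measures ANOVA with a group-by-time interaction for each outcome, and imputation for missing data. It names no analysis population, no all-participant analysis and no sensitivity analysis by attendance. The primary objective (2.1.1) is to find out whether the workshop "is effective in reducing the psychological distress experienced by parents and education staff who work with children with Intellectual Disability". Nothing there limits the question to people who attended every session.

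**The concern.** Under the natural reading, the one result for the primary endpoint answers a narrower question than the objective asks. Change among people who came to all three sessions is a legitimate thing to estimate. Here it would be the only estimate, and nothing in the plan labels it as restricted to full attenders.

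Attendance is a behaviour after baseline and may be related to distress or to perceived benefit. An estimate that conditions on it is open to selection bias when it is read as the effect of offering the workshop to these parents and staff. The documents do not establish the direction of that bias. They describe no randomisation and no untreated control, so no randomised comparison is broken. The estimate rests on within-person change, which makes it depend directly on whose change is counted.

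The rule also discards usable scores. Partial attenders may join the focus group, where six-week questionnaires are collected. The plan would gather those scores and then not use them.

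**Working it through.** **1. Which scores an excluded person can have.** This follows from sections 5.2, 6.1, 6.2 and the questionnaire table in 7.1. On baseline timing, section 5.2 says: "Before the beginning of the first group session, participants will complete the study consent form with the study researchers on an individual basis".

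| Sessions missed | Baseline | After last session | Six weeks | Under 5.2.1 |
|---|---|---|---|---|
| 2 only | yes | yes | yes | excluded |
| 3 only, or 2 and 3 | yes | not by the usual route | yes, in person or by post | excluded |
| 1 (with or without others) | not by the usual route | if at session 3 | possible | excluded |

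The first row is decisive: a complete DASS-21 record is removed because of attendance alone.

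**2. The plan's own figures.** Section 8.1 uses f = 0.25, two groups, three time points, alpha 0.05 and power 0.80. It does not state the correlation between repeated measures. I assume 0.5, with sphericity. The noncentrality is f² × N × 3/(1 − 0.5) = 0.0625 × 28 × 3/0.5 = 10.5, on 2 and 52 degrees of freedom. Power is 0.812 at N = 28 and 0.778 at N = 26, so 28 reproduces. Then 28/(1 − 0.30) = 40. These figures are not in error. The section continues: "This would mean recruiting 40 participants, with the expectation that 12 would be lost to attrition". It does not say whether attendance exclusions are among the 12.

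**3. How many would be excluded (illustration).** The documents give no attendance rates. Let p be attendance per session, independent between sessions.

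- *40 people counted at session 1:* excluded = 40(1 − p²); session 2 only = 40p(1 − p).
- *40 people counted before session 1:* excluded = 40(1 − p³); session 2 only = 40p²(1 − p).

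| p | Excluded, from session 1 | Session 2 only | Share | Excluded, from before session 1 | Session 2 only | Share |
|---|---|---|---|---|---|---|
| 0.95 | 3.9 | 1.9 | 49% | 5.7 | 1.8 | 32% |
| 0.90 | 7.6 | 3.6 | 47% | 10.8 | 3.2 | 30% |
| 0.85 | 11.1 | 5.1 | 46% | 15.4 | 4.3 | 28% |

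**4. How far the estimate could move (illustration).** Let r be the change in those excluded divided by the change in full attenders. At p = 0.90, counted at session 1, full attenders are 0.81 of the 40, session-2-only absentees 0.09 and all excluded 0.19. The ratio below is the full-attender change divided by the change in the wider group.

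| r | Session-2-only absentees recovered: 0.90/(0.81 + 0.09r) | All excluded recovered: 1/(0.81 + 0.19r) | 30% excluded, all recovered: 1/(0.70 + 0.30r) |
|---|---|---|---|
| 0 | 1.11 | 1.23 | 1.43 |
| 0.5 | 1.05 | 1.11 | 1.18 |
| 1 | 1.00 | 1.00 | 1.00 |
| 1.5 | 0.95 | 0.91 | 0.87 |

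The last column is an upper illustration that treats all 12 of 40 as attendance exclusions, which section 8.1 does not say. The columns that recover everyone depend on a model or imputation for scores that were not collected.

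**The case against.** The strongest reply is that the term relevant is undefined and may be meant narrowly, as exclusion only from analyses needing a score the person lacks. Withdrawal option (i) in section 5.2.1 keeps data already collected from people who withdraw, and section 8.2 plans imputation. Both suggest that some incomplete records are meant to stay in.

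The ambiguity is real, which is why the conclusion is put as the most natural reading. But the narrow reading does not fit a rule triggered by missing one or more sessions, because a person who misses only session 2 lacks no score. Option (i) covers people who withdraw and does not restore people who stay and miss a session. Imputation deals with missing values, and scores removed by a rule are not missing. If the narrow meaning was intended, the plan still has to say so. Otherwise the analysis set can be chosen after the data are seen.

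Two further points stand. For change among full attenders, the exclusion defines the target and does not bias it; bias arises when the result is applied to everyone enrolled, which is what objective 2.1.1 invites. The magnitudes rest wholly on assumed attendance and assumed differences in change, so they show scale and predict nothing.

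**Conclusion.** The concern holds. The rule is stated, no all-participant analysis appears anywhere in the document, and the primary DASS-21 result would most naturally be a full-attender estimate set against an objective without that limit.

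Its size cannot be derived from the documents. At an assumed 85 to 95% independent attendance at sessions 2 and 3, about 4 to 11 of 40 would be excluded, and nearly half of those could have complete scores. At 90%, with those excluded changing 0 to 150% as much as full attenders, the full-attender change is 1.11 to 0.95 times the wider estimate if only session-2-only absentees are recovered. It is 1.23 to 0.91 times if everyone is. The direction is unknown.

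The study can run as designed, but the analysis population should be settled before the data are analysed.

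**What to change.** In section 5.2.1, delete the clause that excludes people who miss a session. In section 8.2, add wording such as:

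*The primary analysis includes all consented participants with any available DASS-21 score, whatever their attendance, except those who ask for their data to be removed under option (ii) of 5.2.1. It uses a likelihood-based mixed model over the three time points with the same terms as the planned ANOVA. Participants without a baseline score contribute the scores they have.*

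The exception is needed because option (ii) allows withdrawal from "all aspects of the trial with removal of all previously collected data". The multiple imputation already planned in 8.2, applied to this same population, is an acceptable alternative to the mixed model.

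Keep the full-attender analysis as a labelled secondary analysis. Report how many people attended one, two and three sessions, with their baseline DASS-21 scores.

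The cost is a protocol amendment through the sponsor, the REC and local R&D (section 12.1) and slightly more analysis. No extra participants, visits or measures are needed. The estimated effect may change in either direction.
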